### 3.1.3 Treatment Period

Eligible patients will be treated with an initial dose of two 300-mg infusions (600 mg total) in 250 mL 0.9% sodium chloride each separated by 14 days (i.e., Days 1 and 15) followed by one 600-mg infusion in 500 mL 0.9% sodium chloride every 24 weeks for the remainder of study duration.

Laboratory samples can be taken up to 2 weeks prior to the scheduled study visit. Results should be available prior dosing, except for John Cunningham virus (JCV) and immunoglobulins (Ig) (plasma samples collected and stored centrally), which will be analyzed upon request and CD8 and CD19 (no interference with re-treatment).

For patients presenting with EDSS change at Week 96, the EDSS score will be confirmed after a further 24 weeks.

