- j Plasma samples for anti-JCV antibodies should be taken at baseline and repeated yearly and end of study for storage in a central laboratory. Samples will be analyzed upon request.
- k Patients must have an EDSS score of 0.0 to 4.0 points, inclusive at screening to be eligible. EDSS needs to be confirmed after 24 weeks if EDSS changes from baseline to Week 96
- l Neurological examinations will be used to distinguish relapse in MS from another neurological (non-MS) disorder. Potential relapses should be recorded throughout the treatment period. Investigators will also screen patients for signs and symptoms of PML by evaluating neurological deficits localized to the cerebral cortex, such as cortical symptoms/signs, behavioral and neuropsychological alteration, retrochiasmal visual defects, hemiparesis, cerebellar symptoms/signs (e.g., gait abnormalities, limb incoordination). Patients with suspected PML should be withheld from ocrelizumab treatment until PML is ruled out by complete clinical evaluation and appropriate diagnostic testing. A patient with confirmed PML should be withdrawn from the study.
- m After initiation of study drug, all adverse events should be reported until 96 weeks after the end of the Treatment Period but may be extended in patients whose B-cells take longer to replete. After this period, the investigator should report any serious and non-serious adverse events that are believed to be related to prior study drug treatment (see Sections [5.3.1](#) and [5.6](#)).
- n All patients must receive prophylactic treatment with 100 mg methylprednisolone, administered by slow IV infusion, to be completed approximately 30 minutes before the start of each ocrelizumab infusion, and an antihistaminic drug (e.g., diphenhydramine) approximately 30 – 60 minutes before each infusion of ocrelizumab.
- o Ocrelizumab will be administered as two 300-mg IV infusions in 250 mL 0.9% sodium chloride each on Days 1 and 15 and one 600-mg infusion in 500 mL 0.9% sodium chloride every subsequent dose (i.e., every 24 weeks) for a maximum of 72 weeks. It is anticipated that the patient will need to stay at the hospital or clinic for a full day for the infusion visits.

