3. Check if the first EDSS assessment at a visit (unscheduled or scheduled) on or after the onset date of the relapse is increased by ≥ 0.5 steps from the previous EDSS; or selected FSS domains relevant to the relapse event (pyramidal, ambulation, cerebellar, brainstem, sensory, or converted visual) are increased by ≥ 2 points on one domain or ≥ 1 point on two or more domains. When deriving this step do the following:
 - Take the last EDSS/FSS score before each clinical relapse onset date
 - Take the first EDSS/FSS score on or after each clinical relapse onset date
 - Calculate the difference between the two scores
 - Select clinical relapses where there is an increase of ≥ 0.5 in EDSS or ≥ 2 on one appropriate FSS domain or ≥ 1 on two or more appropriate FSS domains
4. For each relapse that satisfies the 3 criteria above, check if the following relapses are within 30 days (i.e., the onset dates are ≤ 30 days apart). If they are within 30 days, then the later relapses are not PDR.

24-Week Confirmed Disability Progression (CDP) definition

Disability Progression as measured by EDSS is defined a ≥ 1 -point increase in EDSS score from a baseline EDSS score of 0.0–5.5 inclusive, and a 0.5-increase from a baseline EDSS score higher than 5.5. Because of the variability of EDSS, a single measurement at the baseline visit might not provide a sufficiently reliable baseline EDSS. Therefore, using an average score from two separate measurements may improve the reliability of baseline EDSS and the reliability of confirmed disability progression seen in the study. In the analysis of CDP, baseline EDSS is defined as the average of the EDSS scores at the screening and baseline visits (of note, any baseline visits occurring after the first dosing date will be disregarded in the computation of the baseline EDSS score), without rounding. If one of the EDSS scores from the screening or baseline visit was missing, the other was used for baseline EDSS.

Initial progression can happen at any scheduled or unscheduled visit during the 96-week treatment period.

An initial disability progression becomes confirmed if the following conditions are met:

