1. A sustained change in EDSS for a minimum of 24 weeks (-2 weeks) from the initial progression event i.e. the change in EDSS must be sustained at all available (scheduled or unscheduled) visits for a minimum of 24 weeks ($\geq 168-14$ days= 154 days) after initial progression. An “Early Discontinuation” visit can be used as a confirmation visit if it falls into the visit window (defined in the protocol) of any scheduled visit. The EDSS assessments (if any) between the initial disability progression and the confirmation of disability progression should be at least as high as the minimum change required for progression.
2. Scheduled visits within 30 days after the onset of a clinical relapse that meets conditions 1, 2 and 3 of a protocol-defined relapse definition cannot be used for confirmation of disability progression. The confirmation of the disability progression must then be based on the EDSS assessment at the next scheduled visit (which is not within 30 days of a protocol defined relapse).
3. If a patient has a missing assessment at the scheduled visit taking place at 24 weeks (≥ 154 days) after an initial progression, the confirmation of the disability progression must be based on the assessment at the next scheduled visit.

For the patients who have the initial progression at week 96 and roll over to the long term extension of Ocrelizumab study, a confirmation EDSS assessment will be collected in the long term extension (Liberto) study.

Patients who complete the treatment period without confirmed progression of disease will be censored at the date of their last EDSS assessment during the treatment period. Patients with an initial assessment of disease progression who subsequently discontinue

from the study without further assessments will not be considered to have confirmed disease progression, if the discontinuation reason is not lack of efficacy or death. Patients who discontinue from the study due to lack of efficacy or death without confirmed progression of disease will be imputed as having an event (i.e., CDP) at the time of discontinuation.

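### The SAP's CDP derivation names extension-study EDSS only for progressions first seen at Week 96, so later-treatment progressions still unconfirmed at Week 96 are censored in roll-over patients if the text is followed literally

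*SAP*

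**What the plan says.** The definition of 24-week CDP is in SAP 4.4.1.

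- **Onset:** "Initial progression can happen at any scheduled or unscheduled visit during the 96-week treatment period".
- **Interval:** rule 1 asks for "A sustained change in EDSS for a minimum of 24 weeks (-2 weeks) from the initial progression event", which the SAP converts to at least 154 days. The change must hold at every available visit in between.
- **Unusable visit:** if the confirming visit falls within 30 days of a relapse, rule 2 applies: "The confirmation of the disability progression must then be based on the EDSS assessment at the next scheduled visit". Rule 3 says the same when the assessment is missing.
- **Extension data:** one sentence deals with this, and its condition reads "For the patients who have the initial progression at week 96 and roll over to the long term extension of Ocrelizumab study". What it then provides for that group is that the confirming score comes from the extension study.
- **Default:** "Patients who complete the treatment period without confirmed progression of disease will be censored at the date of their last EDSS assessment", with that assessment taken from the treatment period.

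Other places set a wider trigger for collecting the confirmation score. Protocol 3.1.3 says: "For patients presenting with EDSS change at Week 96, the EDSS score will be confirmed after a further 24 weeks". Protocol Appendix 1, footnote k, says: "EDSS needs to be confirmed after 24 weeks if EDSS changes from baseline to Week 96". The SAP repeats footnote k in its Appendix 2, and the End of Study paragraph of its Appendix 1 makes the same exception for an EDSS change at Week 96. None of these depends on when the change was first seen. SAP section 4 states that its analyses take precedence over the protocol's.

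**The concern.** The derivation admits onset at any visit but names a data source beyond Week 96 for one onset time only. A progression first seen at Week 96 has a stated route to confirmation in the extension study. One first seen at Week 80 and still present at Week 96 has none in the derivation, although Week 96 comes too soon to confirm it.

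The exclusion table in SAP 4.4.1 covers only patients who discontinued treatment. A completer with an unconfirmed late progression therefore stays in the denominator as having no CDP and, without other events, as NEDA.

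At stake is a small downward bias in CDP and a matching upward bias in the CDP-free proportion. CDP status would also depend partly on where the patient goes next. A patient who enters safety follow-up has an in-study EDSS at the first follow-up visit (Protocol Appendix 2, footnote f), and a roll-over patient does not. SAP 4.4.2.4 derives CDI in the same way, so it inherits the gap.

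**Working it through.** **Inputs.** The minimum interval is 24 weeks less 2 weeks (SAP 4.4.1). The visit windows at Weeks 72 and 96 are ±14 days (schedule of assessments). N is 750 and the assumed NEDA rate is 30% (SAP 2.3).

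**Step 1: the SAP's own figure.** 24 × 7 − 14 = 154 days, which is 22 weeks. This reproduces.

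**Step 2: latest onset that Week 96 can confirm.** A nominal Week 96 visit is day 672. 672 − 154 = day 518, which is Week 74. With the window, Week 96 can fall on days 658 to 686, so the cut-off runs from day 504 (Week 72) to day 532 (Week 76). Onset after the cut-off cannot be confirmed at Week 96.

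**Step 3: onset at the Week 72 visit.** The nominal gap to Week 96 is 168 days. Within windows it runs from 168 − 28 = 140 to 168 + 28 = 196 days. If Week 72 is *a* days and Week 96 *b* days off target, the gap is 168 + *b* − *a*. It is below 154 when *a* − *b* ≥ 15.

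- Dates uniform and independent over 29 × 29 = 841 day pairs: 14 + 13 + … + 1 = 105 pairs, and 105/841 = 12.5%.
- Dates normal, truncated at ±14 days: 2.1% for SD 5 days and 5.5% for SD 7 days.

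The documents give no distribution of visit dates, so these are assumed cases.

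**Step 4: where each group ends up under a literal reading (roll-over completers).**

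| Initial progression | Can Week 96 confirm it? | Extension EDSS named in the derivation? | Result |
|---|---|---|---|
| At Week 96 | No | Yes | Can be confirmed |
| After about Week 74, before Week 96 | No | No | Censored, no CDP |
| At Week 72, Week 96 less than 154 days later | No | No | Censored, no CDP |
| At Week 72, Week 96 missing or within 30 days of a relapse | No | Rules 2 and 3 point to the next scheduled visit without saying whether an extension visit counts | Undefined |

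**Step 5: scale for NEDA.** The SAP's precision reproduces: the exact interval for 225/750 is 26.7% to 33.4%, half-width 3.3 points. One patient moved from NEDA to not NEDA changes the rate by 1/750 = 0.13 points. As assumed counts only, 5 such patients give 0.67 points and 10 give 1.33 points (30.0% to 28.7%).

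**The case against.** The strongest reply is that the SAP sentence says where data come from and is not an exclusion rule. A reader might infer that the SAP forbids extension EDSS for any other onset. It does not: the word *only* is absent, and rules 1 to 3 do not confine confirmation to the treatment period. Under rule 1 a change that can still be confirmed must persist at an available Week 96 EDSS. Patients in the second and third rows of the table therefore have a change at Week 96 and are due a confirmation score under footnote k, which is in the SAP as well as the protocol. A changed Week 96 score taken near a relapse also triggers it. The censoring sentence applies only to patients whose progression is not confirmed.

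This stands as far as data collection goes, and it means most of the needed scores should exist. It does not settle the derivation. The appendix texts are assessment instructions, and the CDP algorithm does not call for those scores unless onset was at Week 96. Two programmers could assign different CDP status to the same patient.

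A second reply concerns the primary endpoint, and it also stands. Protocol 4.5.4 asks for an EDSS when symptoms suggest relapse, so many unscheduled onsets will come with one. EDSS moves in half-point steps, so crossing the progression threshold will normally meet the EDSS part of the relapse definition. If the other relapse criteria are met, the patient is already not NEDA.

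**Conclusion.** Wrong as written, minor. The derivation in SAP 4.4.1 is narrower than SAP Appendices 1 and 2, Protocol 3.1.3 and Protocol Appendix 1. Followed literally, it leaves roll-over completers with late unconfirmed progressions censored and counted as having no CDP. It also leaves open whether an extension visit can serve as the next scheduled visit.

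The effect is mainly on the CDP proportion and time to CDP, and on CDI by the same route. The NEDA effect is small, at 0.13 points per reclassified patient who is otherwise NEDA. The figures of 12.5% and about 2-6% apply only to Week 72 onsets and rest on assumed visit-date distributions.

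A reader might go further and infer a count of lost events, or treat the 154 of 672 days (23%) before Week 96 as the share of progressions lost. The documents support neither. That ratio is a share of calendar days, and no CDP count, rate of unscheduled onset or roll-over rate is given. Nor do they support a material bias in the primary endpoint.

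**What to change.** In the extension-study sentence of SAP 4.4.1, replace the condition that onset is at Week 96 with: *who have an initial progression during the treatment period that is not yet confirmed at Week 96*. Then state that:

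- confirmation uses the first eligible EDSS at least 154 days after onset, from safety follow-up or the extension study, under rules 1 to 3;
- an extension visit counts as the next scheduled visit under rules 2 and 3;
- patients with no later EDSS are handled by a named rule, for example those who switch to commercial drug and do not enter follow-up.

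Align the wording with the End of Study text in SAP Appendix 1 and footnote k in SAP Appendix 2. CDI then follows through SAP 4.4.2.4.

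The cost is a short edit to the CDP text and wider use of an extension-study data transfer that is already planned. SAP 2.4 already times the primary analysis after the last confirmation visit. Where EDSS is changed at Week 96, the documents already require the confirming score. Where the Week 96 EDSS is missing, an extension score is not guaranteed, so some cases will stay unconfirmed.

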#### **4.6.2 Study Treatment Discontinuation**

Patients must discontinue study treatment if they experience any of the following:

- Ongoing pregnancy or breastfeeding (in case of pregnancy, treatment should be interrupted, and the patient should be monitored for safety; however, the patient can be re-started with the treatment after the pregnancy and breastfeeding period. During pregnancy and breastfeeding, the patient will continue to come for the regular schedule visits as per protocol and will perform all assessments except MRI).
- Life-threatening IRR or serious hypersensitivity reaction
- Active hepatitis B infection
- PML
- Active tuberculosis, either new onset or reactivation

The primary reason for study treatment discontinuation should be documented on the appropriate eCRF. Patient discontinuing the study treatment prematurely will be further monitored in a safety follow-up (see [Section 3.1.4](#)).

Patients who discontinue study treatment prematurely will not be replaced.

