4.4 EFFICACY ANALYSIS

4.4.1 Primary Efficacy Endpoint

Protocol-defined event definition

The definition of a protocol-defined event of disease activity is the occurrence of at least one of the following individual events while on treatment with ocrelizumab:

- A protocol-defined relapse defined as an occurrence of new or worsening neurological symptoms attributable to MS. Symptoms must persist for > 24 hours and should not be attributable to confounding clinical factors (e.g., fever, infection, injury, adverse reactions to medications), and immediately be preceded by neurological stability for at least 30 days.
- 24-weeks CDP based on increase in EDSS while on treatment with ocrelizumab
- A new T1 Gd-enhanced lesion on MRI after week 8
- A new and/or enlarging T2 hyperintense lesion on MRI after week 8

The MRI activity will be calculated on the events starting from week 8 (baseline reset).

Patient without any of this protocol-defined event of disease activity will be considered as NEDA = Yes (no evidence of disease activity).

The primary endpoint, NEDA, as well as the related disease activities components and combinations listed below, will be evaluated on the mITT population based on the following analysis principles:

- Patients, who discontinued treatment prior week 96 due to death or lack of efficacy, will be considered as having evidence of disease activity at the time of treatment discontinuation (e.g NEDA="NO", Relapse="Yes" and CDP="Yes").
- Patients who discontinued treatment for reasons other than death or lack of efficacy with no evidence of disease activity at the time of early treatment discontinuation will be excluded from the analysis as their disease activity status cannot be ascertained.

This is further summarized in the table below:

Endpoint	Patients who discontinued treatment without related disease activities prior week 96 due to:	
	death or lack of efficacy	Other reason than death or lack of efficacy with no evidence of disease activity
NEDA	included with evidence of disease activity (NEDA=NO)	excluded
Relapse	included with evidence of disease activity (Relapse=Yes)	excluded

24-weeks CDP	included with evidence of disease activity (CDP="Yes")	
 • If discontinuation before confirmation, excluded • If discontinuation after confirmation, included when CDP="Yes"
T1 Gd-enhanced lesions after week 8	included with evidence of disease activity	excluded

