4.4.2.2 Time to first protocol-defined event of disease activity

The analyses will include patients in the mITT population.

Patients with early study discontinuation before any disease activity event will be censored at the withdraw date, which is defined in Section 4.6.1. It will be imputed as having an event if discontinuation reason is lack of efficacy or death.

1) Kaplan-Meier analysis of time to first protocol-defined event (refer to section 4.4.1), with estimates (Greenwood 95% confidence intervals using a log-log transformation) of proportion of patients with NEDA determined at week 96 and week 104 (or time of the last event/censoring if that is before week 104). Kaplan-Meier plots will be produced up to the last available time of censoring or event.

2) Life-table analysis will be used to estimate the survival probability of time to first protocol-defined event, with estimates and Greenwood 95% confidence intervals using a log-log transformation by using time intervals which correspond to planned MRI assessments (weeks 24, 48 and 96). Thus, exact time of protocol-defined relapses and 24-weeks CDP will fall within MRI time intervals such as [week 8-week 24), [week 24-week 48), [week48-week96) and [week 96, -end of study]. Life-table plots will be produced.

Sample SAS code can be found below (SAS code is regarded as “draft” until fully validated at the analysis stage):

a) Binary method

```
ods output binomial=dataset BinomialTest=tpvalue;  
proc freq data=event ate;  
    tables eventyn / binomial (level='1') alpha=0.05;  
run;
```

b) Kaplan-Meier method

```
proc lifetest data=dataset method=km conftype=loglog outsurv=surv plots=none notable
STDERR;
time aval*eventyn(1);
run;
```

c) Life -Table method

```
proc lifetest data=dataset method=life conftype=loglog intervals=24 48 96 outsurv=surv
plots=none STDERR;
time aval*eventyn(1);
run;
```

4.4.2.3 Change in EDSS from baseline to week 96

EDSS (actual value, change, percentage change from baseline) will be summarized at each visit (up to week 96) for the ITT population. The change in the eight function scores from baseline up to week 96 will also be summarized for the ITT population.

Additionally, summary statistics will also be presented at week 96 for the following categories of change in EDSS:

- worsened (>0.5),
- stable ($-0.5, 0, 0.5$)
- improved (<-0.5)

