4.6.1 Exposure of Study Medication

Definitions

Dose: Ocrelizumab dose is given as one infusion or two infusions administered 2 weeks apart. Patients will be considered to have received a Dose of treatment if at least part of one infusion of that Dose (either Day 1 or Day 15 for dual infusions) was given. If a Dose is completely missed instead of delayed, the next dose number will be based on the number of previous doses received.

Treatment duration (in weeks) for a patient will be calculated as follows:

$$[(\text{Date of last contact}^* - \text{Date of first dose}) + 1] / 7$$

Treatment duration (in years) for a patient will be calculated as follows:

$$[(\text{Date of last contact}^* - \text{Date of first dose}) + 1] / 365.25$$

*Earliest 1) date of last contact from the study completion page or study early termination page

2) date of death

3) CCOD

Exposure Analysis

Exposure of ocrelizumab will be summarized using descriptive statistics with the following data:

- treatment duration (weeks),
- number of doses received (day 1 and day 15 infusions are considered as one dose)
- total cumulative dose (mg).

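### The lack-of-efficacy and death imputation is triggered by stopping treatment in the primary NEDA rule, but by leaving the study in the CDP definition and three time-to-event rules

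*SAP*

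**What the plan says.** For binary NEDA and each of its components, SAP 4.4.1 keys the imputation to treatment: "Patients, who discontinued treatment prior week 96 due to death or lack of efficacy, will be considered as having evidence of disease activity". Its examples set NEDA to No, relapse to Yes and CDP to Yes, and its table extends the rule to both MRI components.

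The 24-week CDP definition later in 4.4.1 keys it to the study: "Patients who discontinue from the study due to lack of efficacy or death without confirmed progression of disease" are given a CDP at discontinuation. SAP 4.4.2.6 (time to first relapse) and 4.4.2.7 (time to CDP) use the same trigger.

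SAP 4.4.2.2 (time to first event) says: "Patients with early study discontinuation before any disease activity event will be censored at the withdraw date, which is defined in Section 4.6.1". It adds: "It will be imputed as having an event if discontinuation reason is lack of efficacy or death". Section 4.6.1 takes the earliest of death, the clinical cut-off and the "date of last contact from the study completion page or study early termination page". No treatment-stop date appears there.

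Stopping treatment does not mean leaving this study. Protocol 4.6.2 says: "Patient discontinuing the study treatment prematurely will be further monitored in a safety follow-up". SAP section 2 sets that follow-up at 96 weeks or more. Protocol 4.6.1 and 4.6.2 record a separate primary reason for each event, and SAP 4.2 tabulates the two separately.

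**The concern.** Stopping ocrelizumab for lack of efficacy is a plain treatment failure. The SAP expects some of these patients to have no earlier protocol-defined event, because 4.4.1 gives them their own line in the binary output. If such a patient enters follow-up as the protocol intends, no study discontinuation for lack of efficacy is recorded, so the study-based rules impute nothing and the patient is censored. That censoring is informative, and it favours the drug.

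SAP 4.4.2.2 presents its Kaplan-Meier result as a proportion with NEDA at Week 96, so readers will set it beside the primary proportion. The two would differ partly because one word differs between the rules. For binary CDP there are two instructions inside 4.4.1, and a programmer would have to choose between them.

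**Working it through.** **The rules side by side (SAP)**

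| Section | What triggers the imputed event | Otherwise |
|---|---|---|
| 4.4.1, NEDA and components | stopping treatment before Week 96 | other-reason stops without activity are excluded |
| 4.4.1, CDP definition | leaving the study | censored at last EDSS in the treatment period if that period is completed |
| 4.4.2.2, first event | leaving the study early | censored at the 4.6.1 date; no date given for a patient who stays |
| 4.4.2.6, first relapse | leaving the study | censored at last clinical visit up to Week 96 |
| 4.4.2.7, CDP | leaving the study | censored at last EDSS |

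Take a patient who stops treatment for lack of efficacy with no earlier event and enters follow-up. The first row makes her a failure on NEDA, relapse and CDP. None of the other four rows imputes anything.

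**The plan's own figure.** SAP 2.3 assumes 30% NEDA in 750 patients. Exact Clopper-Pearson limits for 225/750 are 26.74% and 33.42%, a half-width of 3.34 points. This matches the stated 26.7% to 33.4% and 3.3.

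**Size for Kaplan-Meier NEDA (illustrative).** The number of lack-of-efficacy stops is not in the documents. Assumptions:
- N = 750, with no other dropout.
- k patients stop for lack of efficacy just after Week 24 or Week 48, with no earlier event, and stay in follow-up.
- The other 750 − k are event-free in 60%, 45% and 30% at Weeks 24, 48 and 96. Only the 30% comes from the plan.
- Under the study trigger, the k patients are censored at the stop.

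Worked case, k = 15, stop after Week 48 (735 other patients):
- Week 24: 735 × 0.40 = 294 events among 750, so S = 456/750 = 0.608.
- Week 48: 735 × 0.15 = 110.25 events among 456, so S = 345.75/750 = 0.461.
- Treatment trigger: the 15 become events, so S = 330.75/750 = 0.441.
- Week 96: 110.25 events among 330.75, a factor of 0.6667.
- Result: 0.441 × 0.6667 = 29.40% with the treatment trigger and 0.461 × 0.6667 = 30.73% with the study trigger. The gap is 1.33 points.

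Under this model, gap = (k/750) × S(96)/S(t), where S refers to the other patients. The ratio is 0.30/0.60 = 0.50 for stops after Week 24 and 0.30/0.45 = 0.667 for stops after Week 48.

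| k (share of 750, rounded) | Binary and KM, treatment trigger | KM, study trigger | Gap, points |
|---|---|---|---|
| 8 (1%) | 29.68% | 30.21-30.39% | 0.53-0.71 |
| 15 (2%) | 29.40% | 30.40-30.73% | 1.00-1.33 |
| 22 (3%) | 29.12% | 30.59-31.08% | 1.47-1.96 |
| 38 (5%) | 28.48% | 31.01-31.86% | 2.53-3.38 |

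With a common treatment trigger, the binary and Kaplan-Meier figures agree exactly in this model.

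**Size for binary CDP.** Assume 10% observed CDP, i.e. 75/750, and that none of the k already has CDP. The study trigger leaves 10.0%. The treatment trigger gives (75 + 15)/750 = 12.0% at k = 15 and (75 + 38)/750 = 15.1% at k = 38.

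**The case against.** The strongest reply is that the SAP uses the two words loosely and means the same event. The schedule footnote on follow-up starts it when a patient discontinues from the study, which there can only mean leaving the treatment period. The 4.4.1 output line for treatment discontinuation also refers to events before withdrawal. This makes a slip of wording plausible, but it does not settle the rule. SAP 4.2 separates the two events, 4.4.2.2 takes its date from study pages through 4.6.1, and no passage equates them. If treatment was meant throughout, the edit simply says so.

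Other parts of the reply limit the scope, and they stand:
- Deaths on treatment end treatment and study together, so they score alike. The gap comes from lack-of-efficacy stops.
- A reader might infer that every other analysis diverges. The 24- and 48-week NEDA proportions follow the 4.4.1 approach, and time to CDI states no imputation of its own.
- A reader might infer that failure of a later DMT would be charged to ocrelizumab. The documents barely support that: 4.4.1 requires events on ocrelizumab, the CDP definition places initial progression within the 96-week treatment period, and 4.4.2.6 and 4.4.2.7 count only events in the treatment period.
- Not every stopper enters follow-up. Switchers to commercial ocrelizumab do not, and consent can be withdrawn.
- Patients who stop for lack of efficacy with no relapse, CDP or lesion may be few. The separate 4.4.1 output line, and sensitivity analysis A in 4.4.4, would help a reader size the NEDA effect, though not the effect on time to relapse or CDP.
- The study is single-arm and mainly descriptive, and the time-to-event analyses are secondary.

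**Conclusion.** The inconsistency is real and should be corrected. The same patient is a failure under one rule and censored without an imputed event under four others, and 4.4.1 gives two answers for binary CDP. Events actually observed still count under every rule.

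The likely size is modest: about 0.5-2 points on Kaplan-Meier Week-96 NEDA if 1-3% stop this way, and 2.5-3.4 points at 5%, against a planned half-width of 3.3. For CDP the contrast is about 12-15% against 10% with 2-5% such stops. All of this rests on assumed stop rates, the assumed event-free pattern, censoring at the stop and, for CDP, no overlap with observed progression.

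A reader might infer a full point of NEDA for each 1% of such stops (k/750, or 1.1 to 2.9 points for 8 to 22 patients). That would require keeping them at risk and event-free to Week 96. SAP 4.4.2.2 does not say so: it gives no censoring date for a patient who stays in the study.

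**What to change.** - **One trigger.** In the CDP definition in 4.4.1 and in 4.4.2.2, 4.4.2.6 and 4.4.2.7, impute on discontinuation of study treatment before Week 96 for lack of efficacy or death. Take reason and date from the treatment-discontinuation eCRF, and use the death date for deaths.
- **Time to relapse.** In 4.4.2.6, make the condition the absence of a protocol-defined relapse. It now refers to confirmed progression, which appears carried over from the CDP rule.
- **Follow-up.** State that a study-withdrawal reason recorded during follow-up does not trigger imputation.
- **Censoring date.** In 4.4.2.2, give a date for patients who stop treatment for other reasons and stay in follow-up, for example the end of the treatment period, in place of the last-contact date in 4.6.1. SAP 2.4 ends that period at Week 96 or a withdraw date, so say there that treatment withdrawal is meant.

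The cost is SAP wording and one derivation flag, since both reasons are already collected. The time-to-event estimates become slightly less favourable. Two differences from the binary analysis remain: other-reason stops without activity are excluded there but censored in the time-to-event analyses, and time to relapse and time to CDP use the ITT rather than the mITT population.
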